5.0 CRITERIA FOR STUDY REMOVAL

- 5.1 Unacceptable adverse event (at the discretion of the treating physician).
- 5.2 Patients unable to tolerate imaging sessions (1 hour total).
- 5.3 Patient choice (patients can withdraw from the study at any time, for any reason).
- 5.4 Patients who's image quality does not meet criteria for primary endpoint analysis due to imaging techniques, scanner settings, patient movement, etc...

6.0 REGISTRATION PROCEDURES

- 6.1 Informed consent is required prior to participation in this study. The study coordinator will inform potential subjects about the study opportunity and ask if they would like to participate. If the patient is interested, they will be given an opportunity to read the informed consent and authorization document specific to the study and ask questions of the study coordinator. The patient will be informed about: 1) the rationale for the study; 2) the logistics of the study; 3) the risks of the study; 4) how the data will be used. Consent will be obtained by the study coordinator. The patient will be given a copy of the consent, and asked to sign another copy for our records.
- 6.2 Patients will be registered for the study after pretreatment evaluation is completed and eligibility criteria are met.
- 6.3 The principal investigator and all key personnel have completed NIH approved institutional and HIPAA training in the conduct of medical research studies

7.0 STATISTICAL CONSIDERATIONS

Spatial overlap between hypoperfused regions of interest (ROIs) on SPECT perfusion (standard) and deficit ROIs on RIBMC will be assessed using Dice similarity coefficient (DSC) (37). *A priori*, we expect a DSC of approximately 0.7 between RIBMC and SPECT ROIs. Indication of larger overlap is desirable for RIBMC validation. Thus, we require a DSC of at least 0.85 (38) and base our sample size calculations on this degree of improvement over *a priori* expectations. With three experts delineating ROIs on RIBMC and SPECT images, we will calculate an average ($n = 3$ experts) DSC per patient. Sample size considerations are based on a t-test for the mean DSC. Castillo et al. (39) provide a working DSC standard deviation of ~ 0.2 , leading to a standard deviation of 0.11 ($= 0.2/\sqrt{3}$) for a mean DSC based on three experts. Assuming a significance level of .05, power of 95%, and standard deviation of 0.11, we find that 15 patients are required to detect a mean DSC of at least 0.85.

Cohort 3. The objective of this study is to collect and process the image data necessary to assess the sensitivity and specificity of our CT Functional Imaging (CT-FI) diagnostic test, consisting of RIBMC and 4DCT-Ventilation, as well as perform receiver operator

characteristic (ROC) analysis. We will conduct a prospective imaging study of 124 patients who present to the Emergency Department with clinical concern for PE and who subsequently undergo chest CTA for further evaluation.

For each case, an expert reader will determine if functional deficits exist within CT-V and RIMBC. The patient will be classified as PE positive if the reader confirms the presence of two or more mismatched segmental or subsegmental defects between CT-V and RIBMC images, and negative otherwise. This CT-FI binary classification indicator will be acquired for each patient. Sensitivity and specificity will be computed with respect to the known (CTA defined) PE diagnosis. A score of 1 (low) to 5 (high) will be assigned to each defect for the ROC evaluation.

Because PE status of the subjects will be known a priori, we may use the statistical theory for estimating a single proportion to determine the sample size needed to estimate the sensitivity or specificity of the CT-FI diagnostic test. Assuming that the sensitivity will be (at least) approximately 80%, we can estimate the true sensitivity with a margin of error of 10% (percentage points) with 95% confidence based on a sample size of 62 positive PE cases. Similarly, the specificity can be estimated with 62 negative PE controls. Concerning the ROC analysis, to determine the sample size needed to detect an "Area under the ROC Curve" (AUC) greater than 50%, it is not necessary to have a prevalence value for PE (since PE status is known a priori). To detect an AUC of at least 70% with Type I error of 1%, power 95% and a 1:1 ratio of cases:controls we require at least 60 cases and 60 controls ([40](#)). Our study is designed to exceed the minimal sample size requirements.

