Figure 4. Study design. 15 patients (cohort 1) found to have segmental or lobar pulmonary emboli on CTA will be recruited for this study. All enrolled subjects will receive 99m Tc-MAA SPECT/CT and 4DCT imaging. The 4DCT acquisitions will be performed at a single setting to evaluate reproducibility, prior to the SPECT/CT imaging. The primary end-point will be the identification and spatial correspondence of pulmonary perfusion defects on the 99m Tc-MAA SPECT/CT and 4DCT derived RIBMC images. All imaging will be performed on the same day. An additional 5 patients (cohort 2) with the same criteria will be recruited. Each will receive 99m Tc-MAA SPECT/CT imaging as before. They will also receive two 4DCT acquisitions, one with normal breathing and the other with positive pressure breathing using BPAP. 62 patients (cohort 3) found to have PE on CTA and 62 patients negative for PE will be recruited for this study. All enrolled subjects will receive a single 4DCT image acquisition. The 4DCT acquisitions will be performed within 48 hours of the CTA.

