9.0 LONG TERM GOALS

This study investigates the use of 4DCT, an imaging study that can be rapidly performed in the emergency department without the need for contrast, in the evaluation of PE.

- 9.1 If successful, this strategy may be tested in further prospective studies in patients who have an unknown PE status.
- 9.2 4DCT RIBMC images may provide a means to detect pulmonary perfusion defects rapidly, at low radiation dose, and in patients who cannot receive intravenous contrast.

9.3 Determine the sensitivity and specificity of 4DCT RIBMC images to detect pulmonary emboli.

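### Cohort 1: Section 7 requires a DSC of at least 0.85 but sizes a t-test against 0.70, which cannot show 0.85, and 15 patients at 95% power does not follow from that test

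*Combined protocol and SAP*

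**What the plan says.** Section 1.0 (Figure 4 legend) sets the end-point: "The primary end-point will be the identification and spatial correspondence of pulmonary perfusion defects" on SPECT/CT and on the images of respiratory-induced blood mass change (RIBMC).

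Section 7.0 turns this into a Dice similarity coefficient. For three readers, "we will calculate an average ($n = 3$ experts) DSC per patient". The expectation is stated first: "we expect a DSC of approximately 0.7 between RIBMC and SPECT ROIs". The plan then says "Indication of larger overlap is desirable for RIBMC validation", and continues: "Thus, we require a DSC of at least 0.85 (38) and base our sample size calculations on this degree of improvement over" the prior expectation.

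On the test: "Sample size considerations are based on a t-test for the mean DSC". On its size: "Assuming a significance level of .05, power of 95%, and standard deviation of 0.11, we find that 15 patients are required", the aim being to detect a mean DSC of 0.85 or more. The SD of 0.11 is given as 0.2/√3.

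The section states no null hypothesis, no sidedness and no rule for deciding whether 0.85 has been reached. Section 9.1 looks ahead: "If successful, this strategy may be tested in further prospective studies".

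**The concern.** There are two separate problems.

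**The requirement and the test do not match.** The plan sets 0.85 as the overlap needed for validation, but the test it sizes measures improvement over 0.70. A significant result supports only a mean above 0.70. The primary end-point could therefore be reported as met on data that exclude the one overlap level the plan asks for.

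**The sample size does not follow from the test named.** A one-mean t-test with the stated inputs does not need 15 patients for 95% power. On those inputs the discrepancy is conservative. But the single power figure hides how strongly power depends on the SD, which the plan reduces from 0.2 to 0.11 by averaging three readers.

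**Working it through.** **Inputs (all Section 7.0).** Expected DSC 0.70, taken here as the null; required DSC 0.85, taken as the alternative; difference 0.15; alpha 0.05; power 95%; SD 0.11 for the three-reader mean; single-reader SD 0.2; n = 15. Sidedness is not given, so both versions are shown.

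**Trying to reproduce 15.** Power of a one-sample t-test is P(T > t(1−α/s, n−1)), plus the negligible lower tail if two-sided. T is noncentral t with n−1 degrees of freedom and noncentrality (0.15/SD)·√n, and s is the number of sides.

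| Test, 95% power | SD | Patients needed | Power at that n |
|---|---|---|---|
| One-sample, two-sided | 0.11 | 10 | 0.969 |
| One-sample, one-sided | 0.11 | 8 | 0.965 |
| One-sample, two-sided | 0.2 | 26 | 0.957 |
| One-sample, one-sided | 0.2 | 21 | 0.953 |

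Rounding is not the cause: the unrounded 0.2/√3 = 0.1155 still gives 10 and 8. A two-sided two-sample t-test with difference 0.15 and SD 0.11 needs 15.01 per group (power 94.99% at 15 per group). That matches the stated figure, but cohort 1 has no second group.

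**Power with 15 patients at a true mean of 0.85.**

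| SD | Two-sided | One-sided |
|---|---|---|
| 0.11 | 99.8% | 99.96% |
| 0.2 | 77% | 87% |

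Power is at least 95% up to SD 0.150 (two-sided) or 0.168 (one-sided).

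**What a significant result means.** The observed mean at which the test becomes significant is 0.70 + t·SD/√15. With SD 0.11, SD/√15 = 0.0284.

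- Two-sided: 0.70 + 2.145 × 0.0284 = 0.761.
- One-sided: 0.70 + 1.761 × 0.0284 = 0.750.
- The 95% CI half-width is 2.145 × 0.0284 = 0.061, so the interval lies wholly below 0.85 when the observed mean is under 0.85 − 0.061 = 0.789.

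Observed means from 0.761 (or 0.750) to 0.789 are therefore significant and exclude 0.85. For example, a mean of 0.77 has CI 0.709 to 0.831.

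This zone closes at larger SDs: above 0.075 × √15/2.145 = 0.135 for the two-sided test, and above 0.15 × √15/(1.761 + 2.145) = 0.149 for the one-sided test. Beyond those values a significant result still does not establish 0.85.

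**Chance of significance when the true mean is below 0.85 (n = 15, SD 0.11).**

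| True mean | Two-sided | One-sided |
|---|---|---|
| 0.75 | 37% | 51% |
| 0.80 | 90.5% | 95.5% |

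**If 0.85 were judged directly.** A lower 95% limit of at least 0.85 needs an observed mean of about 0.85 + 0.061 = 0.911. If the rule were an observed mean of at least 0.85, it would be met only about half the time at a true mean of 0.85.

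**The case against.** The strongest reply is that 0.85 is simply the planning alternative. Detecting a given value is normal sample-size language, no superiority test proves its own alternative, and the plan never says that a p-value against 0.70 will be taken as proof of 0.85. The null of 0.70 is itself an inference. This stands as far as it goes, but the text does not only plan at 0.85: it requires it, for validation. Reading the requirement as an observed mean of at least 0.85 does not help, because the stated 95% power does not apply to that rule.

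Second, the sample-size error is harmless on the plan's own inputs, since 15 exceeds 10 and 8. That stands at SD 0.11. The shortfall appears only if averaging readers reduces the SD less than the plan assumes, and 0.2 is the extreme case of readers who agree fully. With an assumed reader correlation of 0.5, the SD is 0.2 × √((1 + 2 × 0.5)/3) = 0.163 and power with 15 patients is 91% two-sided or 96% one-sided.

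Third, the two consequences do not occur together: one needs an SD below 0.135 (two-sided), the other an SD above 0.150. The first also depends on the true mean. In simulation at SD 0.11 (two-sided), a significant result whose interval excludes 0.85 occurs in about 29% of trials at a true mean of 0.75 or 0.80, and about 2% at 0.70 or 0.85. Both points are correct. They limit how often each problem appears; they do not supply the missing decision rule.

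Fourth, the five cohort 2 patients might also contribute DSC values. With 20 patients and SD 0.2, power would be 89% or 94%. Section 7.0, however, bases its calculation on 15.

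Finally, Section 9.1 is a loose statement of long-term goals that does not define success by DSC. That is fair, and it means the harm lies in what can be claimed from the primary end-point rather than in a documented go/no-go decision.

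**Conclusion.** The concern holds on both parts and should be fixed. The planned test cannot support the overlap level the plan requires. At SD 0.11 it is significant about nine times in ten or more when the true mean is 0.80, which falls short of the requirement. The stated 15 patients at 95% power is not the answer for the test named, which needs 10 or 8; actual power at 15 ranges from 99.8% down to 77% two-sided, or from 99.96% down to 87% one-sided, over SD 0.11 to 0.2.

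The sample is not shown to be too small on the plan's own inputs. The conclusion rests on a null of 0.70, inferred from the improvement wording; on showing both sidedness options because none is given; on setting the observed SD equal to the planning SD for the thresholds; and on treating the plan's two SD figures as the ends of a plausible range. That 15 came from a two-sample calculation is an inference from the matching number.

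**What to change.** Revise the cohort 1 paragraph of Section 7.0, keeping 15 patients:

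1. Name a one-sample t-test on the per-patient mean DSC against 0.70 and choose one sidedness with a matching null: mean equal to 0.70 if two-sided (which also matches a 95% CI), or mean at most 0.70 if one-sided.
2. Limit the test's conclusion to a mean DSC above 0.70, describe 0.85 as the planning alternative, report the mean with its 95% CI, and make no claim of 0.85 from the p-value.
3. Replace the sentence on 15 patients at 95% power with the one-sample power at n = 15 over the SD range. Two-sided: 99.8% (SD 0.11) to 77% (SD 0.2), at least 95% up to SD 0.150. One-sided: 99.96% to 87%, at least 95% up to SD 0.168.
4. If 0.85 is to remain a success criterion, say whether it is judged on the observed mean or on the lower confidence limit, and that the stated power does not cover it.

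Items 1 to 3 cost only wording and one confidence interval. The sponsor gives up claiming a DSC of at least 0.85 from the test alone. Choosing the lower 95% limit under item 4 would be more than a wording change, since the observed mean would then have to reach about 0.91 at n = 15 and SD 0.11.

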With spontaneous tidal breathing, venous return to the right atrium increases with the decrease in intrathoracic pressure (33) and as a consequence pulmonary arterial blood flow to the lungs increases (34). With positive pressure ventilation the opposite occurs, positive-pressure inspiration decreases the pressure gradient for venous return, which decreases venous blood flow, RV stroke volume, and consequently cardiac output (33). We expect the decrease in lung mass, or pulmonary blood, with normal expiration to become an increase in lung mass with positive pressure ventilation as shown in Figure 3 at the right.

In this study, patients found to have new segmental, lobar or greater perfusion defects, will be imaged with 99m Tc-MAA SPECT/CT and 4DCT to compare perfusion with RIBMC defects.

Hypothesis: Thromboembolic pulmonary perfusion defects on 99m Tc-MAA SPECT/CT will coincide with 4DCT RIBMC defect regions.

Summary & Significance

This is a prospective imaging trial of 20 patients with segmental or lobar pulmonary emboli on CTA. Each will receive 99m Tc-MAA SPECT/CT and 4DCT imaging on the same day. Respiratory induced blood mass change (RIBMC) images will be derived from the 4DCT image and quantitatively compared with the SPECT perfusion images. A 5 patient cohort (cohort 2) to test effect of respiratory pressure on RIBMC was added. A 124 patient cohort (cohort 3) to test the sensitivity & specificity of RIBMC was added. Illustrated in Figure 4 below.

[figure not shown]

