3.0 ELIGIBILITY, RECRUITMENT, AND SELECTION

Patients with CTA proven segmental or lobar pulmonary emboli will be recruited for this study. Subjects will not be excluded based on age, gender, gender identity, sexual orientation, economic status, race or ethnicity.

3.1 One cohort of 15 patients and another of 5 patients (20 patients total) with CTA proven segmental or lobar pulmonary emboli will be consented for the study and registered on the protocol. Patients may have started anti-coagulation therapy prior to enrolling.

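### Cohort 1: the 15 patients said to be required for 95% power do not follow from the stated inputs, and the SD of 0.11 rests on an unstated assumption about the readers

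*Combined protocol and SAP*

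**What the plan says.** Section 7.0 (Statistical Considerations) compares perfusion-defect regions on SPECT with deficit regions on the 4DCT-derived blood-mass-change (RIBMC) images. Three experts outline the regions, and their DSCs are averaged to one value per patient. The plan expects a DSC of about 0.7, requires at least 0.85, and says it will "base our sample size calculations on this degree of improvement over" prior expectations. The test is described only in these words: "Sample size considerations are based on a t-test for the mean DSC". The section does not state whether the test is one-sample or two-sample, one-sided or two-sided, or what the null value is.

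For the SD, a cited earlier study is said to "provide a working DSC standard deviation of ~ 0.2". The plan divides this by √3 for the three experts and carries 0.11 forward. It concludes: "Assuming a significance level of .05, power of 95%, and standard deviation of 0.11, we find that 15 patients are required". The target is a mean DSC of 0.85 or more.

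On numbers of patients, the Figure 4 legend in Section 1.0 says "15 patients (cohort 1) found to have segmental or lobar pulmonary emboli on CTA will be recruited for this study", and Section 3.1 has "One cohort of 15 patients and another of 5 patients (20 patients total"). The summary in Section 1.0 opens with "This is a prospective imaging trial of 20 patients with segmental or lobar pulmonary emboli on CTA" and says that the RIBMC images will be "quantitatively compared with the SPECT perfusion images".

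**The concern.** This is the only sample-size justification for cohort 1, which serves the primary objective in Section 2.1. Two things in it do not stand up.

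First, the design has one group, one value per patient, a difference of 0.15 and an SD of 0.11. That is a standardised effect of about 1.36, for which 15 patients looks too many at 95% power.

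Second, dividing by √3 treats the three readings of a patient as independent draws. Three experts outlining the same defect share that patient's true degree of overlap. Averaging readers reduces reader noise; it does not reduce variation between patients.

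The two points pull in opposite directions, so a reader cannot tell whether actual power is above or below the stated 95%. Cohort 3 is sized separately and is not affected.

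**Working it through.** **Inputs, all from Section 7.0.** Difference 0.85 − 0.70 = 0.15; SD 0.11; alpha .05; power 95%; one three-expert mean DSC per patient; no comparison group. Sidedness is not stated, so both are shown.

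**Step 1: try to reproduce 15.** Power of a one-sample t-test comes from the noncentral t distribution with n − 1 degrees of freedom and noncentrality √n × 0.15/SD. With SD 0.11, 0.15/0.11 = 1.364.

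| n | Noncentrality | Power, two-sided | Power, one-sided |
|---|---|---|---|
| 7 | 3.61 | 85.0% | 93.6% |
| 8 | 3.86 | 90.9% | 96.5% |
| 9 | 4.09 | 94.6% | 98.1% |
| 10 | 4.31 | 96.9% | 99.0% |
| 15 | 5.28 | 99.8% | 99.96% |

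The smallest n reaching 95% is 10 two-sided or 8 one-sided.

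Rounding does not explain the gap. 0.2/√3 = 0.1155, which rounds to 0.12 rather than 0.11, but at 0.1155 the answer is still 10 (95.4%) or 8 (95.01%).

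A dropout allowance does not explain it either. Going from 10 to 15 needs about 30% (10/0.70 = 14.3, rounded up to 15). None is stated, and Section 10.2 replaces non-evaluable patients instead.

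**Step 2: what would give about 15?** A two-sample, two-sided t-test at SD 0.11 has noncentrality √(15/2) × 1.364 = 3.73 on 28 degrees of freedom, and power 94.99% at 15 per group. A one-sample two-sided test at alpha 0.01 with SD 0.1155 also gives 15. The first needs a second group that the plan does not have, and the second needs an alpha that it does not state.

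**Step 3: what SD does a three-reader mean have?** The documents give neither the meaning of 0.2 nor a reader correlation, so each reading below is an assumption.

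*Reading A: 0.2 is one reader's SD across patients, and rho is the correlation between readers of the same patient.* SD of the mean = 0.2 × √((1 + 2 rho)/3). If 0.2 is already the SD of a per-patient value, the rho = 1 row applies.

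*Reading B: 0.2 is reader noise only, and a between-patient SD, tau, adds to it.* SD of the mean = √(tau² + 0.2²/3).

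Power at n = 15 against 0.70, normal theory:

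| Assumption | SD of mean | Two-sided | One-sided |
|---|---|---|---|
| A, rho = 0 | 0.1155 | 99.7% | 99.9% |
| A, rho = 0.5 | 0.1633 | 91.1% | 95.8% |
| A, rho = 1 | 0.2000 | 77.1% | 86.8% |
| B, tau = 0.10 | 0.1528 | 94.2% | 97.5% |
| B, tau = 0.15 | 0.1893 | 81.4% | 89.8% |
| B, tau = 0.20 | 0.2309 | 64.8% | 77.2% |

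The largest SD that keeps 95% power at n = 15 is 0.150 two-sided or 0.168 one-sided. Under reading A these correspond to rho of about 0.34 and 0.55.

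These figures are illustrative. DSC cannot exceed 1, and a normal model with mean 0.85 and SD 0.2 puts about 23% of values above 1.

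**Step 4: if cohort 2 is included.** At n = 20, two-sided power under reading A is 99.98%, 97.3% and 88.9% for rho = 0, 0.5 and 1.

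**The case against.** The strongest reply is that the first error is harmless. On the plan's own SD, 15 exceeds what is needed, non-evaluable patients are replaced, and nobody proposes to change the number. That stands as far as it goes: taken alone, the mismatch is a documentation error. It does not rescue the stated 95%, because the surplus exists only at an SD near 0.11, which is the figure in doubt.

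A second reply is that the SD point is inconclusive, since everything turns on what the cited 0.2 measures. That is right, and it limits the claim. A reader might infer from the lower rows of the table that cohort 1 is underpowered. The documents do not support that: with weakly correlated readers and little between-patient variation, power is above 95%. Nor is 77.1% a floor, since reading B goes lower.

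A reader might also infer that 15 was taken from a two-sample calculation. The match is close, but it depends on the SD being cut to 0.11: at 0.1155 the same test needs 17 per group. The origin remains a guess.

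Finally, the counts of 15 and 20 might be read as a contradiction. They are not, because Section 3.1 adds 15 and 5 to reach 20. What is unstated is only whether cohort 2 enters the DSC analysis, which is a separate question about the analysis set.

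**Conclusion.** Wrong as written; minor to moderate severity. On the stated inputs the requirement is 10 patients two-sided or 8 one-sided, not 15, and the discrepancy is on the safe side. This takes the test to be one-sample against 0.70, which the sizing text implies but does not say.

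Separately, the 95% is not established, because 0.2/√3 omits any variation that readers of the same patient share. Depending on what 0.2 measures, two-sided power at 15 patients runs from 99.7% to 77.1% under reading A, and down to 64.8% with the largest between-patient SD tried under reading B. All of these are normal-theory illustrations. They support neither calling the cohort too small nor reducing it.

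One related limit should be stated. Rejecting 0.70 does not show that the mean DSC is at least 0.85, which is what Section 7.0 says it requires. If the true mean were exactly 0.85, the observed mean would reach 0.85 only about half the time.

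**What to change.** Keep 15 patients and restate the cohort 1 paragraph of Section 7.0:

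- **Test.** Name it as a one-sample t-test of the per-patient three-reader mean DSC. Give its sidedness and null value (0.70 is the value the text implies). Add that rejecting the null does not by itself demonstrate the required 0.85.
- **SD.** Say what the 0.2 measures. Use an SD for the three-reader mean that includes between-patient variation, with the formula chosen to match that meaning. Neither formula above should be adopted before this is known.
- **Power.** Replace the 95% claim and the statement that 15 are required with the power at 15 patients over a stated range of that SD. Label it illustrative because DSC is bounded at 1.
- **Analysis set.** State whether the five cohort 2 patients enter the DSC analysis. If they do, give power at 20 as well. The other changes need not wait for this.

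The cost is wording only, with no new patient or scan. The drawback is that one figure of 95% becomes a range that may look less favourable.
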